### ***Data Safety Monitoring Plan***

For each AE, the seriousness, intensity, and relationship to study product will be assessed, documented, and supported by an entry in the subject's medical records. During the study, each

subject will be carefully monitored for any adverse events. After the initial AE/SAE report is completed and sent, the investigator is required to follow each subject at subsequent visits/contacts. As currently practiced, it is planned that all AEs and SAEs will be followed in clinic until: 1) resolution; 2) the condition stabilizes; 3) the event is otherwise explained; or 4) the subject is lost to follow-up.

Drs. [name] and [name], LaCATS Center biostatisticians, will be responsible for all blinding procedures and for subject randomization. Except for the pharmacist who will prepare the capsules, randomization will be blinded to the staff performing the physical measures, metabolic testing, performance of assays, entering or calculating data related to the study and study investigators to assure minimal potential sources of bias. Additionally, sealed randomization envelopes will be sent to the pharmacist for emergency breaking of the blind. The randomization envelopes will be maintained in a secure location with access limited to authorized personnel. Blinding is critical to the integrity of this clinical trial. However, in the event of a medical emergency or pregnancy in an individual subject, in which knowledge of the investigational product is critical to the subject's management, the blind for that subject may be broken by the medical investigator of the trial. This will be done by a request to the pharmacist to break the blind and report the treatment assignment to the medical investigator.

Before breaking the blind of an individual subject's treatment assignment, the investigator should have determined that the information is necessary, i.e., that it will alter the subjects' immediate management. In many cases, particularly when the emergency is clearly not investigational product-related, the problem may be properly managed by assuming that the subject is receiving active product without the need for breaking the blind.

In case of an emergency, the investigator may open the emergency randomization envelope to reveal the identity of the medication for that subject. If such breaking of the blind occurs, the investigator shall notify the IRB immediately. This information, including the reason for the blind being broken must be recorded in the participant chart and regulatory files.

## **STATISTICAL CONSIDERATIONS**

As comparative efficacy of the doses of the extract is not the primary issue in this protocol, power to detect efficacious effects is not specifically evaluated to justify sample sizes. A sample of 18 subjects (three subjects in each of three treatment sequences in each of two cohorts) will be enrolled in the ascending single dose evaluation. Thus, all nine subjects in Cohort 1 will receive the placebo and both 150 and 300 mg doses of the extract; similarly all 9 subjects in Cohort 2 will receive the placebo and both 600 and 900 mg doses of the extract. Before the next cohort is commenced, subjects in the preceding cohort must have received all three treatments and the safety and tolerability data must have been assessed showing tolerance to the doses of naringenin. Based on the pharmacokinetic study done in humans, the sample size (n=6, at each dose) is sufficient to provide a pharmacokinetic profile of naringenin in serum.

The primary outcome will be to determine the effect of the naringenin extract on safety and tolerability based on clinical and biochemical assessment.

The secondary outcome will be to determine the pharmacokinetics of naringenin at the 150 mg and 600 mg doses. Serum concentrations of naringenin will be obtained to assess drug exposure.

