The maximum recommended starting dose (MRSD) for naringenin may be estimated at approximately 135 mg since no adverse events were reported at this dose. The dose escalation scheme recommended for first in human studies is rapid dose escalation initially (MRSD x 2) until the estimated effective dose (600 mg) is reached and then at a more cautious escalation (e.g. x 1.5). The first dose will be 150 mg, the MRSD for the practical purpose of preparing the capsule of an extract from oranges which contains 30% naringenin (Gencor Lifestage Solutions, GE Nutrients Inc., Irvine, CA). HPLC and mass spectrometry verification using a second standard to quantify the naringenin in the extract was conducted by the Rutgers University Botanical core. It was determined that the extract contains 27% naringenin by one method and 29% naringenin by a second method. Therefore, the amount of extract for the 150 mg, 300 mg, 600 mg, and 900 mg doses of naringenin will be calculated based on the average of 28%. According to the United States Department of Agriculture (USDA) database for the flavonoid content of selected foods 150 mg of naringenin could be found in a minimum of approximately four oranges and a maximum of 12 oranges. The orange extract will be calculated to deliver 150 mg, 300 mg, 600 mg, and 900 mg of naringenin. The capsules will be prepared and dispensed by the PBRC pharmacist. The schedule for dosing is provided in Table 1.

Table 1. Ascending Oral Dose Schedule			
	Visit 1	Visit 2	Visit 3
Cohort 1			
Sequence 1 (n=3)	150 mg	Placebo	300 mg
Sequence 2 (n=3)	150 mg	300 mg	Placebo
Sequence 3 (n=3)	Placebo	150 mg	300 mg
Cohort 2			
Sequence 4 (n=3)	600 mg	Placebo	900 mg
Sequence 5 (n=3)	600 mg	900 mg	Placebo
Sequence 6 (n=3)	Placebo	600 mg	900 mg

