### Randomization Procedure and Blinding

Each subject in the cohorts will be randomly assigned one of the relevant treatment sequences in order of enrollment. Treatment sequence assignments will be balanced so that each sequential block will have unique treatment sequences. As an example, the first three enrolled subjects in each cohort will be randomly assigned to one of three distinct treatment sequences, as will enrollees 4-6 and 7-9. As a result, three of the nine subjects in each cohort will be randomly assigned to each of the three treatment sequences. The randomization scheme will be prepared by [name] under the supervision of [name]. Except for the pharmacist who will prepare and dispense the capsules, all study staff and the investigators will be blinded to the randomization.

Table 2. Schedule of Assessments

	Screening	Visit 1a	Visit 1b	Visit 2a	Visit 2b	Visit 3a	Visit 3b
Consent	x						
Height	x						
Weight	x	x		x		x	
Blood Pressure/Pulse/Temperature	x	x		x		x	
Medical History Questionnaire	x						
Pregnancy Test (Urine)*	x						
Concomitant Medications	x						
Chemistry Panel/CBC	x						
Adverse Events		x	x	x	x	x	x
Plasma naringenin			x			x	x
Chemistry Panel/CBC (0 hr)**		x		x		x	
Chemistry Panel/CBC (24 hrs later)**			x		x		x
Naringenin Administration		x		x		x	
IV Placement		x					
Blood Collection at 0, 2, 3, 3.5, 4, 4.5, 6, 8, and 12 hours		x					

\* Women of Child bearing potential

\*\* For Cohort 2 only BUN, AST, and Bilirubin added to Chem 15 panel

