**Visit 1b (½ hour, fasting for at least 8 hours)**

- Subjects will return 24 hours post naringenin administration and blood will be drawn for CBC, Chemistry 15 panel, and to evaluate serum naringenin concentrations.
- Adverse events will be assessed 24 hours after naringenin dosing.

Subjects will return to the clinic to complete Visit 2 no less than seven days after the completion of Visit 1.

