### ***Events meeting the definition of an AE:***

- Any abnormal laboratory test results (clinical chemistry) or other safety assessments (e.g., vital signs measurements), including those that worsen from baseline, and felt to be clinically significant in the medical and scientific judgment of the investigator.
- Exacerbation of a chronic or intermittent pre-existing condition including either an increase in frequency and/or intensity of the condition.
- New conditions detected or diagnosed after study treatment administration even though it may have been present prior to the start of the study.
- Signs, symptoms, or the clinical sequelae of a suspected interaction.
- Signs, symptoms, or the clinical sequelae of a suspected overdose of either study treatment or a concomitant medication (overdose per se will not be reported as an AE/SAE).

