### ***Reporting Procedures***

The reporting of SAE's will follow the standards of practice as outlined by the PBRC IRB in the investigator's responsibility policy (pages 4 and 5). Once the investigator determines that an event meets the protocol definition of an SAE, the SAE will be reported to the IRB within 24 hours. If the investigator does not have all information regarding an SAE, the investigator will not wait to receive additional information before notifying the responsible parties of the event and completing the appropriate forms. An assessment of causality at the time of the initial report will be provided. Email transmission of the SAE data collection tool will be the preferred method to transmit this information followed by notification by telephone and/or fax. A copy of the SAE report will also be sent to the institution officials. New or updated information will be recorded in the originally completed data collection tool. The investigator will submit any updated SAE data within 24 hours.

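### Within Cohort 2, one serious or severe related adverse event at 600 mg triggers no automatic hold before other subjects receive 900 mg

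*Combined protocol and SAP*

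**What the plan says.** **Between cohorts.** Statistical Considerations requires, before the next cohort begins, that "subjects in the preceding cohort must have received all three treatments and the safety and tolerability data must have been assessed showing tolerance". Safety and tolerability adds one interim safety summary, covering Cohort 1.

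**Within Cohort 2.** Table 1 gives every subject placebo, 600 mg and 900 mg. Sequence 5 takes 900 mg at Visit 2; Sequences 4 and 6 take it at Visit 3. The stated condition for moving on is an interval for that subject: "Subjects will return to the clinic to complete Visit 2 no less than seven days after the completion of Visit 1", with the same rule from Visit 2 to Visit 3. Cohort 2 visits are described as similar to those of Cohort 1 apart from dose and three added laboratory tests.

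**Allocation.** "Each subject in the cohorts will be randomly assigned one of the relevant treatment sequences in order of enrollment", and "the first three enrolled subjects in each cohort will be randomly assigned to one of three distinct treatment sequences". One of the first three enrollees is therefore in Sequence 5. Enrollment pace is not stated.

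**Safeguards in place.**
- Adverse events (AEs) are checked at each dosing visit and at 24 hours, and the laboratory panel is repeated at 24 hours (Table 2).
- A laboratory abnormality counts as an AE when "felt to be clinically significant in the medical and scientific judgment of the investigator".
- For a serious adverse event (SAE), "the SAE will be reported to the IRB within 24 hours".
- The study physician reviews tolerability, and a subject with a significant AE is withdrawn (Minimizing risks).
- The Stopping Rules halt dosing for a death, the same SAE in two subjects, the same severe related AE in two subjects, or when the investigator decides a review is needed. Dosing resumes only if investigator and IRB both agree.

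**The concern.** The primary objective is safety at escalating single doses, and 900 mg is the highest. The step to 600 mg waits for a whole cohort's data. The step to 900 mg waits for no stated number of subjects and no recorded decision.

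Withdrawal protects the subject who had the event. The gap concerns the other subjects in the cohort. If one of them has an SAE, or a severe AE judged related, after 600 mg, whether the rest go on to 900 mg is left to judgment. The two-subject triggers cannot be met on 600 mg data while only one subject has had that dose. Because the investigators are blinded to sequence, they also do not know which Visit 2 dose is the first 900 mg dose, so no event in the trial's conduct prompts them to stop and look.

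**Working it through.** **1. The plan's own figure.** 3 subjects × 3 sequences × 2 cohorts = 18, and 9 subjects per active dose. This reproduces.

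**2. When 600 and 900 mg are given in Cohort 2 (Table 1, three per sequence).**
- 600 mg: Visit 1 in Sequences 4 and 5 (6 subjects); Visit 2 in Sequence 6 (3).
- 900 mg: Visit 2 in Sequence 5 (3); Visit 3 in Sequences 4 and 6 (6).

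Every subject has 600 mg before 900 mg, so the number exposed to 600 mg before the first 900 mg dose is at least one.

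**3. How many subjects have 24-hour data on 600 mg before the first 900 mg dose?** The earliest permitted timing is Visit 1a on day 0, Visit 1b on day 1, Visit 2a on day 1 + 7 = 8, and Visit 3a on day 16. Blocks of three give (3!)³ = 216 equally likely orders. In each order I took the first 900 mg dose in any sequence and counted subjects whose 600 mg dose plus one day fell strictly before it. The enrollment paces are assumptions.

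| Enrollment pace | Range | Mean |
|---|---|---|
| All nine on one day | 6 | 6.0 |
| One per day | 4–7 | 5.5 |
| One per two days | 2–5 | 3.8 |
| Two per week | 1–4 | 2.6 |
| One per week | 1–3 | 1.83 |

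At one per week the counts of 1, 2 and 3 arise in 72, 108 and 36 orders: (72×1 + 108×2 + 36×3)/216 = 396/216 = 1.83, and 72/216 = 33% give a count of 1. If 24-hour results arriving on the very day of the first 900 mg dose are also counted, the orders become 36, 72 and 108, with mean 504/216 = 2.33, and the range at two per week becomes 2–5.

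**4. What a one-subject and a two-subject trigger would see.** With *n* subjects exposed to 600 mg and true event rate *p* (assumed), P(at least one) = 1 − (1 − p)ⁿ and P(at least two) = 1 − (1 − p)ⁿ − np(1 − p)ⁿ⁻¹. The second is an upper limit for the plan's rule, which also needs the two events to be the same.

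| p | n = 2: ≥1 | n = 2: ≥2 | n = 6: ≥1 | n = 6: ≥2 |
|---|---|---|---|---|
| 1% | 2.0% | 0.01% | 5.9% | 0.15% |
| 5% | 9.8% | 0.3% | 26% | 3.3% |
| 10% | 19% | 1.0% | 47% | 11% |

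For scale, zero AEs in 18 subjects at 1000 mg gives a one-sided 95% upper limit of 1 − 0.05^(1/18) = 15.3% for any AE. Serious or severe related events should be rarer than that.

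**The case against.** The strongest reply is that this is a deliberate design. Escalation within a cohort is per subject: each sequence gives the lower dose first, at least seven days earlier, and the quoted half-life is about 2.3 hours. Cohort 1 has the same structure, since Sequence 2 takes 300 mg at Visit 2 after 150 mg, a larger relative step. The investigator's discretionary trigger can act after one subject, and restarting needs IRB agreement. An earlier study gave 1000 mg, with an additive to raise bioavailability, to 18 subjects with no AEs reported. If all nine subjects start close together, several will have had 600 mg before anyone takes 900 mg.

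All of this stands, and it limits the concern. The 1000 mg experience is weaker support than it looks: it was in hepatitis C patients, rests on a communication, and the protocol does not say it used this orange extract. What remains is that after one serious or severe related event the hold is optional.

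Two stronger readings are tempting. A reader might infer that the plan breaks its own principle of rapid escalation "until the estimated effective dose (600 mg) is reached and then at a more cautious escalation (e.g. x 1.5". The documents do not support this: that caution is expressed as step size, and 900/600 = 1.5 complies. A reader might also infer that 900 mg will follow a single subject's 600 mg dose. The text permits that, but it arises only under slow enrollment, and no pace is stated.

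**Conclusion.** The concern holds in a limited form. The plan reviews tolerance between cohorts only, and its fixed stopping rules, death aside, need two subjects with the same event. A single SAE or severe related AE at 600 mg therefore imposes no automatic hold on the remaining 900 mg doses. It would be wrong to say that the step is unmonitored: data are collected and reviewed, and the investigator may stop dosing at any time.

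The size depends on enrollment pace and minimum visit intervals, both assumed here. With near-simultaneous starts the concern is small. At one enrollment per week the first 900 mg dose rests on about two subjects' 600 mg data, and a two-subject rule then has almost no chance of being met. This is an inexpensive improvement to consider, not a defect that undermines the trial.

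**What to change.** Add to Stopping Rules:

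> If any one subject has an SAE, or a severe AE judged related to study product, further dosing in that cohort is held until the un-blinded safety review is complete.

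The existing condition for resuming, agreement of investigator and IRB, would apply unchanged. Add also that, before Visit 2 and Visit 3 dosing, the medical investigator, blinded to sequence, records a review of the AE and 24-hour laboratory data then available. In Cohort 2 the blinded review before Visit 2 can be interpreted when subjects move through visits together, because Visit 1 contains only 600 mg (6 subjects) or placebo (3). Wording the rule by cohort also covers 150 to 300 mg.

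**Cost.** No new data are needed. The downside is an occasional pause, sometimes for an event on placebo. At an assumed rate of 1% per dose, placebo included, the chance of at least one hold is 1 − 0.99⁹ = 8.6% over nine Visit 1 doses and 1 − 0.99²⁷ = 24% over all 27 doses in a cohort.

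**Optional.** The sponsor could also hold all Visit 2 doses in Cohort 2 until every enrolled subject still in the study has completed Visit 1b. Without dropouts this secures six subjects at 600 mg before any 900 mg dose, and the seven-day interval is a minimum, so waiting is allowed. The first enrollee would wait an extra (8 × 3.5 + 1) − 8 = 21 days at two enrolled per week, or (8 × 7 + 1) − 8 = 49 days at one per week. The last enrollee's schedule need not move. A long wait might call for a repeat pregnancy test, which Table 2 lists only at screening. This is a trade-off for the sponsor; the one-subject hold does not depend on it.

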### **Safety and tolerability.**

Dose safety will be investigated by compiling by treatment (e.g. 150 mg dose, 300 mg dose, placebo) a list of adverse events such as frequency of headaches, nausea, vomiting. The study physician in consultation with the coordinator will review and determine safety and tolerability. The frequency of these events will be counted and compared with the placebo group. The

cohorts will be run in series. There will be an interval of up to four weeks between the two cohorts. During this time an interim analysis will be conducted and a safety summary of adverse events for Cohort 1 will be compiled and reviewed by the investigators.

### Stopping Rules

Dosing within a cohort will be stopped and further dosing will be halted until un-blinded safety information can be reviewed in the event that:

- A death occurs
- Two or more subjects experience the same SAE following administration of study product.
- Two or more subjects in each cohort experience the same severe study product-related AE following administration of study product
- Based on AEs, laboratory findings, or clinical findings the Investigator determines that review of pertinent safety information is required.

Dosing may only resume if, after review of safety information, both the Investigator and IRB agree that it is safe to proceed.

**Pharmacokinetics of naringenin extract.** Pharmacokinetics of orally administered naringenin will be analyzed using a non-compartmental model. The maximal concentration ( $C_{max}$ ), time to peak ( $T_{max}$ ), half-life ( $T_{1/2}$ ), area under the serum concentration versus time curve ( $AUC_{0-24hr}$ ) and apparent oral clearance ( $Clearance_{oral} = Dose/AUC_{0-24hr}$ ) for each subject will be determined and the means for subjects given 150 mg and 600 mg doses will be calculated. Pairwise comparisons of 150 mg, 600 mg and placebo will be tested with a linear model for each of the parameters ( $C_{max}$ ,  $T_{max}$ ,  $T_{1/2}$ ,  $AUC_{0-24hr}$  and  $Clearance_{oral}$ ) across all time points. All analyses will use SAS Version 9.4 software (SAS Institute Inc., Cary NC).

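### Stopping rule 3 is mis-worded: read literally it needs two cases in both cohorts, so that rule could not trigger during Cohort 1; a within-cohort count is the likely intent

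*Combined protocol and SAP*

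**What the plan says.** The Stopping Rules section lists four triggers, numbered here in the order of its bullets.

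- **Lead-in:** "Dosing within a cohort will be stopped and further dosing will be halted" until unblinded safety data have been reviewed.
- **Rule 1:** a death.
- **Rule 2:** "Two or more subjects experience the same SAE following administration of study product". It has no cohort qualifier.
- **Rule 3:** "Two or more subjects in each cohort experience the same severe study product-related AE following administration of study product".
- **Rule 4:** the investigator decides, from adverse events, laboratory results or clinical findings, that a review is needed.

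Dosing resumes only if the investigator and the IRB both agree.

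On timing, Safety and tolerability says that the "cohorts will be run in series", and that in the interval between them "a safety summary of adverse events for Cohort 1 will be compiled and reviewed by the investigators". Statistical Considerations adds: "Before the next cohort is commenced, subjects in the preceding cohort must have received all three treatments". The safety and tolerability data "must have been assessed showing tolerance to the doses of naringenin". Each cohort has nine subjects. No other section restates rule 3 or says how its cases are counted.

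**The concern.** A halting rule has to tell staff when it is met. Attached to a count in a trigger condition, *in each cohort* sets the requirement separately for every cohort, so all of them must satisfy it. In a trial that doses its cohorts in series, that makes the rule unusable in the first cohort. In the second, which receives 600 and 900 mg, the rule would depend on what happened at 150 and 300 mg.

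Safety and tolerability are the primary objective. A fixed count exists so that a halt does not rest on judgement alone. At stake is whether rule 3 does that job as written.

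**Working it through.** **1. The two readings against the timeline**

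| Stage | Literal reading (two cases in both cohorts) | Within-cohort reading |
|---|---|---|
| During Cohort 1 | Cannot be met: no Cohort 2 subject has been dosed | Met at the second matching case |
| During Cohort 2 | Needs two Cohort 2 cases and two earlier Cohort 1 cases of the same event | Met at the second matching case in Cohort 2 |

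The literal reading also sits badly with the condition for opening Cohort 2. Two matching severe, related events in Cohort 1 would weigh heavily against a finding of tolerance, so the situation in which the literal rule could operate would seldom arise.

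**2. Which reading is intended**

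- The lead-in defines the action within one cohort.
- Randomization Procedure and Blinding uses the phrase for each cohort taken separately: "the first three enrolled subjects in each cohort will be randomly assigned to one of three distinct treatment sequences". The pregnancy-test criterion, the opening line of Clinic Visits and the payment section use it in the same way.
- Rule 2 has no cohort qualifier, so the qualifier in rule 3 must mean something. A within-cohort count is the sense that fits the lead-in.

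**3. Size of the difference, for rule 3 alone**

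Inputs:

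- Cohort size: 3 subjects × 3 sequences = 9, and 9 × 2 cohorts = 18, which matches the plan's total.
- Per-subject risk *p* of one given severe, related event over the two active doses: not in the documents. Values of 1%, 2%, 5% and 10% are assumed. The two human studies described under Rationale for Naringenin Dose reported no adverse events in 6 + 18 = 24 subjects. The one-sided 95% upper bound is 1 − 0.05^(1/24) = 11.7%. That bound is for any adverse event, in other populations and formulations, so it does not support a value as high as 5% or 10% for one specific severe, related event.

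Formula for the within-cohort count, with X ~ Binomial(9, *p*):

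P(X ≥ 2) = 1 − (1 − *p*)^9 − 9*p*(1 − *p*)^8

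- *p* = 0.01: 1 − 0.9135 − 0.0830 = 0.0034
- *p* = 0.02: 1 − 0.8337 − 0.1531 = 0.0131
- *p* = 0.05: 1 − 0.6302 − 0.2985 = 0.0712
- *p* = 0.10: 1 − 0.3874 − 0.3874 = 0.2252

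Under the literal wording, the probability during Cohort 1 is 0 at every *p*. By the end of Cohort 2, with equal and independent risks, it is the square of the within-cohort figure.

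| Assumed *p* | Within-cohort count, either cohort | Literal, during Cohort 1 | Literal, by end of Cohort 2 |
|---|---|---|---|
| 1% | 0.3% | 0 | about 0.001% |
| 2% | 1.3% | 0 | about 0.02% |
| 5% | 7.1% | 0 | 0.5% |
| 10% | 22.5% | 0 | 5.1% |

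The last column ignores the tolerance condition for opening Cohort 2, which would lower it further.

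**The case against.** The strongest reply is that nobody running this trial would apply the literal reading. The lead-in governs every bullet, the phrase means each cohort taken separately elsewhere in the protocol, and the literal rule would hardly ever operate. Most of this stands: the within-cohort count is the likely intent and probably the likely practice. It does not remove the defect, because the meaning of a safety threshold should be in its own wording.

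A second reply is that other safeguards cover the gap. They do so in part:

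- Rule 4 allows a halt on any finding, but at the investigator's discretion.
- Minimizing Risks withdraws a subject with a significant adverse event, but does not pause dosing for the others.
- The review between cohorts comes after Cohort 1 dosing has ended, so it cannot stop dosing inside a cohort.

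Two stronger readings are tempting, and the documents support neither:

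- A reader might infer that Cohort 1 has no route to a halt, so that the fix would raise the chance of a pause from zero to the probabilities above. Rules 1, 2 and 4 operate throughout Cohort 1. Two matching severe, related events are just what rule 4 would be used for. The added chance of a pause is therefore smaller than those figures, by an amount the documents do not fix.
- A reader might infer that rule 3 is the only fixed-count halt for severe, related events that are not serious. Assessment of Intensity is unclear here. It first separates severe events from SAEs, then describes a Severe Adverse Event as one meeting an SAE outcome. On the second sentence, rule 2 would already cover such events and little would depend on rule 3.

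**Conclusion.** The point holds as a minor wording correction to an operative safety rule. Taken literally, rule 3 could not trigger during Cohort 1, and in Cohort 2 it would need two earlier Cohort 1 cases. That follows from the text and the serial design and needs no assumption.

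The size is illustrative only. It rests on assumed risks of 1% to 10%, the same for all nine subjects and independent between them, and it describes rule 3's own trigger probability. No analysis, estimate or sample size is affected. The documents do not show that the protocol leaves Cohort 1 unprotected or that staff would misapply the rule.

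**What to change.** In the third bullet of Stopping Rules, replace *in each cohort* with *within a cohort* and leave the rest of the sentence as it is. Rule 2 needs no change.

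The cost is one phrase of protocol text, with no change to visits, sample size or analysis. If staff already count within a cohort, practice stays the same. If they would have applied the literal wording, the downside is a slightly higher chance of a temporary pause for safety review, which ends once the investigator and the IRB agree that dosing may resume.

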## STUDY DESIGN

This is a placebo-controlled, ascending treatment crossover design trial with washout periods of at least one week.

**Primary objective:** Evaluate the effect of single oral administration of naringenin at four escalating doses on safety and tolerability in healthy volunteers.

**Secondary objective:** Evaluate the pharmacokinetics of naringenin at low (150 mg) and high (600 mg) doses to test if changes in serum concentrations are proportional to the dose, by assessing naringenin drug exposure ( $AUC_{0-24}$ ).

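### The secondary objective is dose proportionality of AUC0-24, but the planned PK analysis tests equality between doses and names no result, ratio or interval that answers it

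*Combined protocol and SAP*

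**What the plan says.** The Study Design section gives the secondary objective a definite question about the 150 and 600 mg doses: "to test if changes in serum concentrations are proportional to the dose, by assessing naringenin drug exposure", with AUC0-24 as the exposure measure. Statistical Considerations restates it more loosely: "The secondary outcome will be to determine the pharmacokinetics of naringenin at the 150 mg and 600 mg doses", followed by a sentence on obtaining serum concentrations to assess exposure.

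The only PK analysis text is the paragraph on pharmacokinetics of naringenin extract, placed after the Stopping Rules. Cmax, Tmax, T1/2, AUC0-24 and oral clearance (defined as Dose/AUC0-24) "for each subject will be determined and the means for subjects given 150 mg and 600 mg doses will be calculated". It continues: "Pairwise comparisons of 150 mg, 600 mg and placebo will be tested with a linear model for each of the parameters", "across all time points". It does not mention proportionality, dose normalisation, a ratio, an interval or the scale of analysis, and it does not say which of the five comparisons answers the objective.

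On design, Statistical Considerations gives 150 and 300 mg to Cohort 1, and "similarly all 9 subjects in Cohort 2 will receive the placebo and both 600 and 900 mg doses of the extract". The Safety and tolerability section adds that the "cohorts will be run in series". On numbers: "the sample size (n=6, at each dose) is sufficient to provide a pharmacokinetic profile of naringenin in serum".

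**The concern.** Five things do not fit together.

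- **AUC and Cmax.** The null is equality between doses. Under exact proportionality that null is false by a factor of 4, so its p-value does not address the question.
- **Clearance.** Equal clearance is the same statement as a 4-fold AUC, so this comparison is relevant. But it is one of five undesignated tests, with no ratio or interval and no rule for reading a non-significant result.
- **Placebo contrasts.** Clearance has no meaningful value at dose zero, and T1/2 and Tmax have none without measurable drug. Placebo AUC and Cmax can be computed but say nothing about proportionality.
- **Time points.** The five parameters are one number per subject per profile, so a comparison over time points is undefined.
- **Cohorts.** The 150 and 600 mg doses go to different subjects, in cohorts run one after the other and randomised only within cohort. The crossover therefore gives no within-subject or randomised 150 v 600 mg comparison, and the analysis text does not say so.

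At stake is the secondary conclusion. The report could present a significant AUC difference, or a non-significant clearance difference, as an answer on proportionality when neither is one.

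**Working it through.** **Inputs from the documents.** Dose ratio 600/150 = 4. Clearance = Dose/AUC0-24. PK sample size 6 per dose.

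**Reproducing n=6.** Table 2 places the full sampling series at Visit 1a only. In Table 1, 150 mg is given at Visit 1 in Sequences 1 and 2, and 600 mg in Sequences 4 and 5. That is 2 × 3 = 6 per dose, which agrees with the stated figure. The Pharmacokinetic Testing section ties sampling to the dose rather than the visit; read alone it could imply 9 per dose.

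**Assumptions.** The documents give no CV for AUC and no alpha for the PK tests. I assume log-normal AUC, the same CV at both doses (40%, range 20% to 60%) and a two-sided 5% level. Then sd_log = √ln(1+CV²) = 0.198, 0.385 and 0.555 at CV 20%, 40% and 60%.

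**Step 1: what each null means.** CL600/CL150 = (600/AUC600)/(150/AUC150) = 4/(AUC600/AUC150). This equals 1 only when the AUC ratio is 4. Equal clearance is therefore proportionality, and equal AUC is a gross departure from it.

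**Step 2: chance of p<0.05.** Pooled two-sample t-test on the raw scale, 6 v 6, 200,000 simulated trials per scenario:

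| Test | True AUC ratio | CV 20% | CV 40% | CV 60% |
|---|---|---|---|---|
| AUC | 4 (proportional) | 100% | 99.7% | 90% |
| AUC | 2 | 99.95% | 75% | 42% |
| Clearance | 4 (proportional) | 5% | 5% | 4% |
| Clearance | 3 | 61% | 20% | 11% |
| Clearance | 6 | 88% | 35% | 17% |
| Clearance | 2 | 99.9% | 75% | 42% |

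The AUC test is usually significant both when exposure is proportional and when it only doubles, except at high CV. The clearance test has the right null and finds a doubling often at CV 40% or less, but it misses moderate departures unless the CV is low.

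**Step 3: what an interval would show.** The 90% CI for the dose-normalised 600/150 ratio is the estimate multiplied and divided by exp(t × sd_log × √(2/n)), with t on 2n − 2 = 10 degrees of freedom. At CV 40%: exp(1.812 × 0.385 × √(2/6)) = 1.50. The factor is 1.23 at CV 20% and 1.79 at CV 60%. With a true ratio of 1 and CV 40%, the expected interval is about 0.67 to 1.50.

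**Step 4: if there were 9 per dose.** At CV 40%, clearance power is 30% (3-fold) and 52% (6-fold). The CI factor is exp(1.746 × 0.385 × √(2/9)) = 1.37 (1.18 to 1.58 for CV 20% to 60%). The conclusion does not change.

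**Step 5: cohort differences (illustrative).** Suppose the cohorts differ in true clearance by a factor k for reasons other than dose. At n=6 and CV 40%, the nominal 90% CI then covers the true dose ratio in 87% of trials (k = 1.10) or 76% (k = 1.25). The values of k are mine. They show only that the interval does not account for cohort differences.

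**The case against.** The strongest reply is that the relevant test is already planned. Clearance is defined as the inverse of dose-normalised AUC0-24 and is compared between 150 and 600 mg. Means by dose are also planned, so a ratio could be read off them. Nothing says that a non-significant clearance difference will be taken as proportionality. Where AUC only doubles, the clearance test has 75% power at CV 40%, so AUC and clearance read together would often expose the departure. The cohort structure is visible in Table 1. In a small trial with a safety primary objective, what remains could be called clarification.

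Much of this stands. The gap is one of designation and reporting, not of missing data, and the difference tests are the whole of the planned inference but not of the planned output. The cohort caveat and the profile count are clarifications. But a ratio of means without an interval does not show how little 6 per dose can establish, and the plan does not say that clearance is the parameter that decides.

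A second objection is that the simulated AUC test has two groups, whereas the plan puts placebo in the comparison. True, but this works the other way. If placebo AUC is near zero with negligible variance (an assumption), a three-group model with 6 subjects per group (15 degrees of freedom) borrows that small variance. The chance of a significant AUC difference under mere doubling then rises from 75% to 89% at CV 40%, and from 42% to 62% at CV 60%.

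The CVs are assumptions, and clearance power runs from 11% to 88% across them for the 3-fold and 6-fold cases. That range is itself a reason to report an interval.

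**Conclusion.** The concern holds and should be fixed. As written, the analysis does not say which result answers the stated secondary objective. The test on the named measure, AUC0-24, cannot answer it. The one comparison that can, clearance, is planned in a form whose most likely outcome for moderate departures is an uninterpretable non-significant result, unless variability is low. The placebo contrasts for clearance, T1/2 and Tmax, and the reference to time points, cannot be carried out meaningfully.

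The sizes rest on log-normal AUC, equal CVs of 20% to 60% that the documents do not supply, and 6 profiles per dose. The mismatch between the AUC null and the objective rests on none of these. The descriptive PK parameters and the primary safety objective are unaffected.

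**What to change.** In the PK analysis paragraph:

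1. Name one result as the answer to the secondary objective: the 600/150 ratio of dose-normalised geometric mean AUC0-24, from a linear model on log values with a 90% CI, where 1 means proportional. This is the planned clearance comparison written as a ratio (geometric mean clearance at 150 mg over that at 600 mg), so it adds no test. Give the same ratio for Cmax as supporting information. A 95% interval would also serve if fixed in advance.
2. Present it as estimation. State that neither a non-significant difference nor an interval that includes 1 will be read as showing proportionality.
3. State that the ratio compares different subjects in cohorts run in series and randomised only within cohort, so its interval does not cover cohort differences.
4. Take placebo out of the parameter comparisons, report placebo concentrations descriptively, and delete the reference to time points.

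In Statistical Considerations, word the secondary outcome to match the Study Design objective, and state the number of full profiles per dose consistently with the Pharmacokinetic Testing section.

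The cost is analysis wording and a few lines of SAS, with no new subjects, samples or data. The interval will be visibly wide, about ×/÷ 1.23 to 1.79 for CV 20% to 60% at 6 per dose, and it cannot remove cohort differences.
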